**LIST OF ABBREVIATIONS AND DEFINITION OF TERMS**

Abbreviation	Definition
ATC	Anatomic and Therapeutical Class
CI	Confidence Interval
CRF	Case Report Form
CRO	Clinical Research Organization
DREES	Direction de la Recherche, des Etudes, de l'Evaluation et des Statistiques
EQ-5D-5L	EuroQol 5 dimensions 5 levels
GDP	Gross Domestic Product
GP	General Practitioner
HZ	Herpes Zoster
PHN	Post Herpetic Neuralgia
PRO	Patient Reported Outcomes
Q1	1st quartile
Q3	3rd quartile
SAP	Statistical Analysis Plan
SD	Standard Deviation
SS	Social Security
ZBPI	Zoster Brief Pain Inventory

## DOCUMENT HISTORY

Version	Date	Section	Description	Author
0.1	01-Aout 2017		Initial release	PPD (Stat Process)
0.3	06-Oct 2017		Post CS version	PPD (Stat Process)
0.4	23-Oct-2017		Post CS version V2	PPD (Stat Process)
1.0	03-Nov-2017		Final version	PPD (Nukléus)

## 1. OVERVIEW AND STUDY PLAN

This statistical analysis plan (SAP) provides a comprehensive and detailed description of strategy and statistical technique to be used to realize the analysis of data for study POSTHER – EPI-ZOSTER-020 BOD FR (201926).

### 1.1 Objectives

The primary objective is to evaluate Herpes Zoster (HZ)-related and Post Herpetic Neuralgia (PHN)-related direct medical costs and indirect costs during a 9 months period (overall, by gender and classes of age) among people  $\geq 50$  years old in France.

Secondary objectives are:

- To describe HZ and PHN pain severity during a 9 months period (overall and by classes of age)
- To evaluate the impact of HZ and PHN on the quality of life of patients during a 9 months period (overall by gender and by classes of age)

## 1.2 Study design

This is an observational, prospective cohort study of patients  $\geq 50$  years old with a Herpes Zoster (HZ) diagnosis, carried out by a French national random sample of community first line practitioners concerned by HZ diagnosis: general practitioners (GPs), dermatologists and ophthalmologists.

Patients  $\geq 50$  years old with a primary HZ diagnosis (no earlier case of HZ) were included in the **HZ cohort** during a one-year inclusion period.

[figure not shown]
All patients of the HZ cohort presenting Post Herpetic Neuralgia (PHN) 3 months (defined as the presence of HZ-associated severe "worst" pain: pain  $\geq 3$  from ZBPI item "worst pain") after HZ rash onset symptoms were included secondarily in the **PHN cohort**.

Patients of the HZ cohort were followed-up for 3 months using phone interviews with a nurse at 1 month (+/- 3 days) and 3 months (+/- 1 week) after HZ rash onset.

Patients of the PHN cohort were followed up for another 6 months period using phone interviews with a nurse a 6 months (+/- 1 week) and 9 months (+/- 1 week) after HZ rash onset.

Page

Graph 1: Study Design

### 1.3 Determination of sample size

#### 1.3.1 Subjects

The study was initially designed to include 250 cases of HZ with 40 cases of PHN expected (hypothesis of 16% of PHN at M3).

For quantitative variables, such as costs and utilities, the precision is a function of the variability of the variable. With a sample of 250 subjects, a precision between  $\pm 3.1\%$  and 24.8% is obtained for a standard deviation between  $\frac{1}{4}$  and 2 times the mean. With 40 subjects and still a standard deviation between  $\frac{1}{4}$  and 2 times the mean, a precision of the mean between  $\pm 7.7\%$  and 62.0% is obtained.

**Table 1: Precision of a 95% CI for a continuous variable, taking into account the standard deviation and sample size, according to the normal distribution of the mean**

Sample size (n)	Standard Deviation (SD as % of the mean)					
	1/4	2/4	3/4	1	1,5	2
250	3,1%	6,2%	9,3%	12,4%	18,6%	24,8%
40	7,7%	15,5%	23,2%	31,0%	46,5%	62,0%

$\pm 1,96 \times SD / \sqrt{n}$ , with SD the standard deviation and n the sample size.

GlaxoSmithKline

POSTHER

**Statistical Analysis Plan**

**Version: Final version 1.0**

**Date: 03 nov 2017**

Page

### 1.3.2 *Physicians*

In the study of the General Practitioners' sentinel electronic surveillance network, the average yearly number of cases reported by each GP was 3.31 (95%CI 2.82; 3.80) (Gonzales Chiappe S, 2010).

For the Posther study, it was assumed that GPs and specialists would include at least a mean number of 1 and 2 subjects respectively, for an initial 6 months period. With this hypothesis, a random sample of 170 GPs, 20 dermatologists and 20 ophthalmologists could include 250 cases of HZ.

In cohort studies, some participating physicians are not active, especially with scarce patients such as HZ cases. Assuming a rate of two thirds of active participation, 210 GPs, 30 dermatologists and 30 ophthalmologists should be recruited.

## 1.4 Modifications from the protocol

### 1.4.1 *Physicians' recruitment*

Due to the slowest rate of inclusion of patients than expected, the inclusion period was lengthened from 6 months to 12 months.

For the same reason, the random sample of potential investigators was extended to the list of medical professionals managing HZ provided by the OpenRome organization. Open Rome, thanks to a professionals' ad hoc network pre-positioned, livened up by an independent technical team, is capable of

- mobilizing the actors of health of first appeal around the surveillance of the environment,
- leading at any time investigations of ground, locating factors, exposed people and counting the cases

### 1.4.2 *Number of subjects*

Despite the corrective actions conducted in the patients' recruitment process, the final number of subjects expected to be included in the study is around 100.

With a sample of 100 subjects, a precision between  $\pm 4.9\%$  and 39.2% is obtained for a standard deviation between  $\frac{1}{4}$  and 2 times the mean.

**Table 2: Precision of a 95% CI for a continuous variable, taking into account the standard deviation and a sample size of 100 patients, according to the normal distribution of the mean**

Sample size (n)	Standard Deviation (SD as % of the mean)					
	1/4	2/4	3/4	1	1,5	2
100	4,9%	9,8%	14,7%	19,6%	29,4%	39,2%

$\pm 1,96 \cdot SD / \sqrt{n}$ , with SD the standard deviation and n the sample size.

All the analyses will be performed as initially planned, except when the number of patients in a subgroup of interest is below 5.

## 2. POPULATIONS

### 2.1 Patients' population

To be included in the HZ cohort, patients had to fulfill all the following criteria:

- Patients with a first visit for a diagnosis of HZ and who attend the clinic within two weeks of the start of HZ symptoms (defined as unilateral pain accompanied by a unilateral rash without alternative diagnosis)
- Without any history of previous HZ
- $\geq 50$  years old
- Who agree to participate and signed informed consent
- Able to understand the study, to complete self-administered questionnaires (alone or with the help of a relative) and to answer phone interviews

All patients of the HZ cohort presenting PHN 3 months after onset of the HZ rash onset should be included in the PHN cohort.

PHN was defined as the presence of HZ-associated severe pains:  $\geq 3$  of the ZBPI item "worst pain", completed during the phone interview of the patient at 3 months  $\pm 1$  week.

### 2.2 Patients' analyzable population

Patients included with

- All Inclusion criteria met are selected in the analyzable patients population of the HZ cohort.

Among them, patients with

- An answer  $\geq 3$  at Item 3 of the ZBPI "Please circle the figure that describes at best the worst pain you felt within the last 24 hours" (from 0 – no pain, to 10 the most horrible pain you could imagine) at M3

are selected in the analyzable patients population of the PHN cohort.

### 3. COLLECTED DATA

Table 3: List of procedures

	HZ COHORT		PHN COHORT		
	Inclusion	M1 ± 3 days	M3 ± 1 week	M6 ± 1 week	M9 ± 1 week
Initiation activities that will be managed by the site					
Aggregated demographic data	X				
Signed patient agreement	X				
Eligibility criteria	X				
Medical history	X				
Clinical Diagnosis of HZ, Procedure performed or prescribed	X				
HZ characteristics and co-morbidity	X				
HZ severity					
Healthcare resources prescribed Direct and indirect cost	X				
Patient booklet					
Report week by week HZ-related healthcare resources used between Inclusion and M1	X				
ZBPI self-administered questionnaire	X				
EQ-5D-5L Health state self-administered questionnaire	X				
Follow up activities that will be managed during the phone interviews					
ZBPI questionnaire		X	X	X	X
EQ-5D-5L Health State		X	X	X	X
Healthcare resources used Direct and indirect cost		X	X	X	X
Sent reminder to patient for phone interview 8-12 days before phone date		X	X	X	X
Sent the patient booklet Report week by week HZ-related healthcare resources used during the next three months			X	X	X

#### 3.1 Inclusion visit

For each patient included in the HZ cohort, physicians had to fill a paper medical questionnaire with the following information collected during patient's visit:

- Inclusion criteria
- Date of visit
- Demographics: Gender, Month and Year of birth, Occupational status - HZ characteristics:
  - o date of HZ rash onset o prodromal symptoms Yes / No (prodromal pain, hyperthermia, malaise, other – specify) o rash localization (left side, right side): head, ophthalmic zona, HZ oticus, neck, chest, arm, forearm, hand, abdomen, pelvis, thigh, leg, foot
  - o complications Yes / No:
    - cutaneous: viral dissemination, bacterial surinfection, other - specify

- ocular: lost of corneal sensitivity, keratitis, scleritis, uveitis, iridocyclitis, other - specify
- neurological: transverse myelitis, meningo-encephalitis, paralysis of cranial nerve, paralysis of peripheral nerve, syndrom of Ramsay Hunt, persistance of HZ pain, other – specify
- visceral: extension of the viral infection (bronchitis, oesophagitis, cystitis,...), viral dissemination (pneumonia, arthritis, hepatitis,...), other - specify
- ear
- other – specify
- associated comorbidities (Yes / No):
  - emotional problems, stress, depression
  - alcoholism ○ tobacco consumption ○ diabetes
  - renal insufficiency / dialysis ○ hepatic pathology
  - hepatitis C under active treatment within 12 months before HZ diagnosis
  - VIH infection with a CD4 rate < 350/ $\mu$ l or past opportunistic infection or other manifestation of AIDS at time of HZ diagnosis
  - Cancer – Solid tumor (ongoing chemotherapy or radiotherapy, or active or metastatic disease within 6 months before HZ diagnosis)
  - Malignous hemopathies (ongoing chemotherapy or radiotherapy, or active or metastatic disease within 6 months before HZ diagnosis)
  - Organ transplant within 12 months before HZ diagnosis or for 12 months or more with an ongoing anti-rejection treatment
  - Hematopoïetic cells or bone marrow transplantation before HZ diagnosis or for 12 months or more with an ongoing anti-rejection treatment
  - Active auto-immune pathology under treatment ( $\geq$  5 mg/day or more of corticoids or immunosuppressors) within 12 months before HZ diagnosis: rheumatoid arthritis, ankylosing spondylitis, lupus erythematosus, psoriasis, Crohn's disease, ulcerative colitis
  - Other comorbidity – specify
- Ongoing immunosuppressive treatment (Yes / No): oral or parenteral corticotherapy; chemotherapy or cytostatic treatment; monoclonal or polyclonal antibody; anti-rejection treatment – immunosuppressive treatment (cyclosporine, tacrolimus, sirolimus); other - specify

### 3.2 Patient Reported Outcomes (PRO)

#### 3.2.1 Zoster Brief Pain Inventory (ZBPI)

Developed in 2004, the ZBPI is an Herpes Zoster specific questionnaire based on the brief pain inventory (Coplan PM, 2004).

It is organized in four main chapters:

- Pain associated with HZ within the last 24 hours. If yes: place of pain, side of pain (left or right), pain at front or back

- Assessment of pain from 0 (no pain) to 10 (most horrible pain you could imagine) for:
  - o Worst pain within the last 24 hours
    - o Lowest pain within the last 24 hours
    - o Global pain within the last 24 hours
    - o Pain now
- Treatments for pain (yes/no) and relief of pain with these treatments within the last 24 hours (from 0% no change to 100% complete relief)
- Burden of pain from 0 (no burden) to 10 (complete burden) for:
  - o Global activity
  - o Mood
  - o Walking ability
  - o Usual work
    - o Relationship with others
  - o Sleep
  - o Zest of life

The questionnaire is filled by the patient during the inclusion visit on a paper form.

At 1 month, 3 months (and 6 and 9 months for the PHN cohort), the questionnaire is directly answered by the patient during the phone interview.

A postal mail or email are sent 8-12 days before the planned interview to provide self-administered questionnaires (ZBPI and EQ-5D 5L) for the interview, as well as a patient booklet that should be used by the patient to report weekly HZ-related healthcare resources used during the last three months.

### 3.2.2 EQ-5D-5L

The EuroQol Group is a network of international multidisciplinary researchers devoted to measurement of health status.

The EuroQol 5 dimensions 5 levels (EQ-5D-5L) questionnaire is a standardised measure of health status developed by the EuroQol Group, in order to provide a simple, generic measure of health for clinical and economic appraisal (EuroQol Group, 1990).

The EQ-5D-5L comprises the following 5 dimensions: mobility, self-care, usual activities, pain/discomfort and anxiety/depression. Each dimension has 5 levels: not at all, mild, moderate, severe, extreme or leading to incapacity.

In addition, the patient needs to score from 0 (the worst imaginable health state) to 100 (the best imaginable health state) his present health state.

The questionnaire is filled by the patient during the inclusion visit on a paper form.

At 1 month, 3 months (and 6 and 9 months for the PHN cohort), the questionnaire is directly answered by the patient during the phone interview.

### 3.3 Health care resources

#### 3.3.1 *Medical treatments for HZ and its consequences*

Treatments prescribed and taken by the patient are recorded at several time frames:

- Treatments bought by the patient before the inclusion visit (recorded by the physician on the CRF at inclusion visit)
- Treatments prescribed by the physician at the end of the inclusion visit - Treatments taken by the patient, recorded during phone interviews:
  - o Between inclusion and 1 month
  - o Between 1 month and 3 months
  - o Between 3 months and 6 months (for the PHN cohort)
  - o Between 6 months and 9 months (for the PHN cohort)

The following items are recorded, for each treatment: treatment name, dosage (mg), number of boxes, number of tablets contained in one box.

#### 3.3.2 *Sick leave for HZ and its consequences*

The prescription of sick leave is recorded at inclusion visit by the physician (yes, no), with the prescribed number of days.

Sick leaves actually made by the patient are recorded during phone interviews, with the number of days of sick leave for each sick leave, and the total number of days of sick leave on the period:

- o Between inclusion and 1 month
- o Between 1 month and 3 months
- o Between 3 months and 6 months (for the PHN cohort)
- o Between 6 months and 9 months (for the PHN cohort)

#### 3.3.3 *Medical visits after inclusion for HZ and its consequences*

At the end of inclusion visit, the physician recorded whether he sent the patient to a specialist: neurologist, dermatologist, ophthalmologist, other – specify; as well as the reason for sending: pain, cutaneous lesions, complications, other – specify.

Visits actually made by the patient are recorded during phone interviews, for visits to GPs on one hand, and for visits to specialists on the other hand (neurologist, dermatologist, ophthalmologist, other specialist – specify) with the date of visit for each of them, and the total number of visits on the period:

- Between inclusion and 1 month ○ Between 1 month and 3 months
- Between 3 months and 6 months (for the PHN cohort) ○ Between 6 months and 9 months (for the PHN cohort)

### ***3.3.4 Emergency room visits for HZ and its consequences***

Visits to emergency rooms actually done by the patient are recorded during phone interviews, with the date of the visit and the reason for the visit (pain, cutaneous lesions, complications, other – specify) for each of them, and the total number of visits to emergency rooms on the period:

- Between inclusion and 1 month ○ Between 1 month and 3 months
- Between 3 months and 6 months (for the PHN cohort) ○ Between 6 months and 9 months (for the PHN cohort)

### ***3.3.5 Hospital stays for HZ and its consequences***

At the end of inclusion visit, the physician recorded whether he sent the patient to the hospital; as well as the reason for sending: pain, cutaneous lesions, complications, other – specify.

Hospital stays actually made by the patient are recorded during phone interviews, with the number of days of the stay and the reason for the stay (pain, cutaneous lesions, complications, other – specify) for each of them, and the total number of days of stay at hospital on the period:

- Between inclusion and 1 month ○ Between 1 month and 3 months ○ Between 3 months and 6 months (for the PHN cohort) ○ Between 6 months and 9 months (for the PHN cohort)

#### 4. GENERAL STATISTICAL APPROACH

All statistical analyses will be descriptive and will provide description of the data along with 95% 2-sided CIs.

The quantitative variables are summarized using the following parameters:

- Number of non-missing data,
- Number of missing data,
- Mean,
- Standard deviation,
- Median and first & third quartiles
- Minimum,
- Maximum.

The qualitative variables are summarized using the following parameters:

- Number of non-missing data,
- Number of missing data,
- Counts and percentages

Missing data or unknown responses are not counted in the percentages, but numbers of missing data are presented in the results tables.

### 5. ANALYSIS OF PATIENT DATA

#### 5.1 Analysis variables

##### 5.1.1 Clinical Variables

All data collected by the investigator at inclusion are considered as clinical variables.

In addition, the following criteria are computed:

- Age: rounding to integer of number of months between month of birth / year of birth and month of visit date / year of visit date, divided by 12
- Age in classes: [50 – 60[, [60 – 65[, [65 - 70[, [70 – 80[, >=80 years old
- Time between start of rash and inclusion date (Days): (inclusion date – rash date) / 365.25
- Number of body sites of rash (number of sites ticked among head, ... feet)

- Total number of sites of rash (number of sites taking into account the side left or right) - Patient immunocompromised: if at least one of the following condition is met:
  - o Active auto-immune pathology under treatment ( $\geq 5$  mg/day or more of corticoids or immunosuppressors) within 12 months before HZ diagnosis
  - o VIH infection with a CD4 rate  $< 350/\mu\text{l}$  or past opportunistic infection or other manifestation of AIDS at time of HZ diagnosis
  - o Cancer – Solid tumor (ongoing chemotherapy or radiotherapy, or active or metastatic disease within 6 months before HZ diagnosis)
  - o Malignous hemopathies (ongoing chemotherapy or radiotherapy, or active or metastatic disease within 6 months before HZ diagnosis)
  - o Organ transplant within 12 months before HZ diagnosis or for 12 months or more with an ongoing anti-rejection treatment
  - o Hematopoïetic cells or bone marrow transplantation before HZ diagnosis or for 12 months or more with an ongoing anti-rejection treatment o Ongoing immunosuppressive treatment is Yes
  - o At least one treatment prescribed by investigator or declared as taken by patient at any interview amongst ATC class L04 (Immunosuppressants)

Other comorbidities recorded as free texts are standardized before analysis. Other free texts are standardized as well when necessary.

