#### 5.2.2.2 Patients' data

All analyses (see section 5.1) will be conducted globally for the HZ and for the PHN cohorts. The analysis of the HZ cohort will also be performed according to:

- gender
- classes of age: < 70 years / ≥70 years

Due to the very small sample size expected for the PHN cohort, no further subgroup of this cohort will be considered.

Patients' profiles will be produced for each of the patients of the PHN cohort.

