#### 5.2.2.2.1 Clinical variables

Clinical variables (see section 5.1.1) will be analyzed in a descriptive way according to the general statistical approach described in section 4.

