## 6. DATA HANDLING CONVENTIONS

Wordings (clear text) will be standardized before analysis. The listings will be submitted to the coordinating center for validation before use in the analysis.

Missing month of dates will be considered as 06 for durations and intervals computations.

Missing days of dates will be considered as 15 for durations and intervals computations.

When the unit is year, the result will be divided by 365.25.

When the unit is month, the result will be divided by 365.25/12 (=30.4375).

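### Rash-to-inclusion time is labelled in days but computed in years, and the age-rounding rule could place patients aged 69 years 6–11 months in the ≥ 70 group

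*SAP*

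**What the plan says.** **Time since rash.** Section 5.1.1 of the SAP defines "Time between start of rash and inclusion date (Days): (inclusion date – rash date) / 365.25". Section 6 sets the general convention for durations: "When the unit is year, the result will be divided by 365.25". It gives 30.4375 as the divisor for months and none for days. Section 5.2.2.2.1 sends the variable to the descriptive tables: "Clinical variables (see section 5.1.1) will be analyzed in a descriptive way".

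**Age.** The inclusion form collects "Gender, Month and Year of birth, Occupational status" (section 3.1), so day of birth is not available. Section 5.1.1 computes age as "rounding to integer of number of months between month of birth / year of birth" and the month and year of the visit, divided by 12. The next line gives "Age in classes: [50 – 60[, [60 – 65[, [65 - 70[, [70 – 80[, >=80 years old". Section 5.2.2.2 repeats the HZ cohort analyses by gender and by "classes of age: < 70 years / ≥70 years". The SAP does not say whether rounding is to the nearest integer or downward, or whether the classes and subgroups are built from the rounded or the unrounded age.

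**The concern.** The first item is a contradiction within a single line: the label says days and the formula returns years. A programmer who follows the SAP produces a wrong table, and one who produces the right table departs from the SAP.

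The second item is an incomplete rule. Rounding, in its ordinary sense, is to the nearest integer, whereas an age limit such as ≥ 70 is normally read as completed years. If the rounded value feeds the subgroups, the older group in effect starts at about 69.5 years. The 70-year split is the only age subgroup in which the HZ cohort analyses are repeated, and the primary objective in section 1.1 asks for costs by age class. The rule therefore reaches the main results, if only slightly.

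**Working it through.** **1. Time from rash to inclusion**

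Inputs: the formula in section 5.1.1, the divisors in section 6, and the entry rule in section 2.1 that patients present no more than two weeks after symptoms began. That rule is used here as the approximate range, 0–14 days.

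| True delay (days) | As written: days / 365.25 | Without the divisor |
|---|---|---|
| 1 | 0.0027 | 1 |
| 3 | 0.0082 | 3 |
| 7 | 0.0192 | 7 |
| 14 | 0.0383 | 14 |

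The as-written column is in years, which is what section 6 says the divisor yields. If results are shown to two decimals (an assumption, as the SAP text sets no number of decimals), the 15 possible values from 0 to 14 days collapse to five, 0.00 to 0.04.

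**2. Age at the class limits**

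Nearest-integer rounding (half up) of months/12, compared with completed years:

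| Age in months | months/12 | Nearest | Floor |
|---|---|---|---|
| 833 (69 y 5 m) | 69.42 | 69 | 69 |
| 834 (69 y 6 m) | 69.50 | 70 | 69 |
| 839 (69 y 11 m) | 69.92 | 70 | 69 |
| 840 (70 y 0 m) | 70.00 | 70 | 70 |

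Exactly six monthly ages, 834 to 839, cross the 70-year limit, all upward. The same happens at 60 (from 714 months), 65 (from 774) and 80 (from 954).

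**3. How many patients**

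The SAP gives no age distribution, so four were assumed and simulated with 4 million ages each. A check by hand for the uniform cases: 6 months out of 40 × 12 = 480 is 1.25%, and 6 out of 45 × 12 = 540 is 1.11%.

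| Assumed age distribution | At 834–839 months | Share ≥ 70 (nearest rounding) | Movers as share of ≥ 70 group | Any change among the five classes |
|---|---|---|---|---|
| Uniform 50–90 | 1.24% | 51.40% | 1.24/51.40 = 2.4% | 5.00% |
| Uniform 50–95 | 1.11% | 56.75% | 1.11/56.75 = 2.0% | 4.45% |
| 50 + 45 × Beta(2, 3) | 1.84% | 41.99% | 1.84/41.99 = 4.4% | 6.59% |
| 50 + 45 × Beta(1.5, 3) | 1.52% | 30.19% | 1.52/30.19 = 5.0% | 6.17% |

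Section 1.4.2 expects about 100 patients, so 1.1–1.8% is one or two people. The last column adds all four limits and concerns only the five baseline classes. Only the limit at 70 bears on the repeated cost, pain and quality-of-life analyses.

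**4. Effect on a subgroup mean**

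Let p be the movers' share of the ≥ 70 group. If movers cost on average what the < 70 group costs, the observed ≥ 70 mean is (1 − p) × mean(≥ 70) + p × mean(< 70). It moves toward the younger group's mean by p times the difference, which is 2–5% of that difference.

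**5. Other readings of the age rule**

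With floor(months/12), or with unrounded months/12 used for the subgroups, the six-month shift is zero. What remains is 0.09–0.15% of patients wrongly counted as ≥ 70, because day of birth is not collected. Rounding the month count first and then dividing by 12 also leaves these patients below 70.

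**The case against.** On the unit error there is little to say in defence. Section 6 gives divisors only for years and months, so a careful programmer would infer that days take none. A mean delay of 0.02 days against a two-week entry window would probably be caught when the output is checked. That limits the harm but leaves the instruction wrong.

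On age the objection is stronger. The shift requires both that rounding means nearest and that the classes use the rounded value, and the SAP states neither. Age and age class are listed as separate variables, and half-open intervals suit a continuous age as well as an integer one. The percentages rest on assumed distributions. The 2–5% figure also assumes that patients just under 70 cost what the average younger patient costs. If cost changes gradually with age, they resemble the older group more closely and the figure overstates the effect. Using unrounded age would serve as well as floor.

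All of this stands, and it is why the age point is put conditionally. It does not remove the need for the SAP to say which rule applies.

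**Conclusion.** The concern holds, at minor severity.

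- **Unit error: certain, with no assumption needed.** As written, all location and spread summaries of rash-to-inclusion time are too small by a factor of 365.25. The damage stops at that one descriptive variable.
- **Age rule: under-specified.** On the nearest-integer reading, with subgroups built from rounded age, one or two of about 100 patients would be placed in the ≥ 70 group while still 69. The subgroup mean would move by 2–5% of the between-group difference, subject to the assumed age distributions and the assumption about movers' costs. On the other readings nothing moves and only the wording needs correcting.

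**What to change.** In section 5.1.1:

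1. Define time from rash to inclusion, in days, as inclusion date minus rash date, with no divisor.
2. Define age as completed years, floor(months/12). Note that it is approximate only in the birthday month because day of birth is not collected. State that the five classes and the < 70 / ≥ 70 subgroups both use this value. Basing both on unrounded months/12 would give the same grouping.

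The cost is two one-line corrections to the SAP and the matching program lines. No new data are needed.
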